3.2.1 Primary Endpoint

The primary efficacy endpoint variable is Objective Response Rate (ORR), defined as the percentage of patients with objective response according to RECIST 1.1 by ICR using the evaluable for response analysis set (all patients who have received at least 1 dose of IPs and have measurable disease at baseline according to ICR).

The secondary endpoint variable of ORR using the investigators assessment of RECIST and based on the full analysis set will also be analysed.

An additional sensitivity analysis of ORR will be performed using the ICR data summarized using the full analysis set.

ORR will only include patients whose response has been confirmed by a second scan at least 4 weeks after the initial response. A confirmed response of CR/PR means that a response of CR/PR is recorded at 1 visit and confirmed by repeat imaging not less than 4 weeks after the visit when the response was first observed with no evidence of progression between the initial and CR/PR confirmation visit. Data obtained up until progression, or last evaluable assessment in the absence of progression, will be included in the assessment of ORR. Patients who receive a subsequent anti-cancer therapy (note that for this analysis radiotherapy is not considered a subsequent anti-cancer therapy) and then respond will not be included as responders in the ORR (i.e. both visits contributing to a response must be prior to subsequent therapy for the patient to be considered as a responder).

In the case where a patient has two non-consecutive visit responses of PR, then, as long as the time between the 2 visits of PR is greater than 4 weeks and there is no PD between the PR visits, the patient will be defined as a responder. Similarly, if a patient has visit responses of CR, NE, CR, then, as long as the time between the 2 visits of CR is greater than 4 weeks, then a best response of CR will be assigned.

Table 6 below outlines scenarios for the first and subsequent visit responses and the rules that will be followed to determine whether such patients would be counted in the numerator of ORR for the primary analysis and their classification for Best Objective Response (BOR) for the primary analysis. BOR is included as supportive data for the ORR endpoint.

Table 6 Confirmed ORR and BoR criteria

First time point	Second time point	Confirmed Responder for ORR	Best objective response
CR	CR	Yes	CR
CR	PR	Scenario not possible, CR can only be followed by CR PD, NE	SD, PD or PR ^a
CR	SD	Scenario not possible, CR can only be followed by CR PD, NE	SD provided minimum criteria for SD duration met, otherwise, PD
CR	PD	No	SD provided minimum criteria for SD duration met, otherwise, PD
CR	NE	No	SD provided minimum criteria for SD duration met, otherwise NE
PR	CR	Yes	PR
PR	PR	Yes	PR
PR	SD	No	SD
PR	PD	No	SD provided minimum criteria for SD duration met, otherwise, PD
PR	NE	No	SD provided minimum criteria for SD duration met, otherwise NE
CR/PR	Second timepoint not reached at time of analysis	No*	SD provided minimum criteria for SD duration met, otherwise NE
CR/PR	Patient withdrew consent before second timepoint reached	No*	SD provided minimum criteria for SD duration met, otherwise NE
NE	NE		NE

CR = complete response, PR = partial response, SD = stable disease, PD = progressive disease, and NE = inevaluable. (Eisenhauer et al 2009).

* Note for the interim analysis, ORR will include both confirmed and unconfirmed responses, so patients in these scenarios would be counted as responders.

^a If a CR is truly met at first time point, then any disease seen at a subsequent time point, even disease meeting PR criteria relative to baseline, makes the disease PD at that point (since disease must have reappeared after CR). Best response would depend on whether minimum duration for SD was met (scan at least 7 weeks post-baseline). However, sometimes 'CR' may be claimed when subsequent scans suggest small lesions were likely still present and in fact the patient had PR, not CR at the first time point. Under these circumstances, the original CR should be changed to PR and the best response is PR.

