1.4 Study Design

This is an open label, Phase IIb, single arm, multi-center study to assess the efficacy and safety of the combination of cediranib and olaparib in platinum resistant relapsed high grade serous, high grade endometrioid or clear cell ovarian, fallopian tube or primary peritoneal carcinoma who have received at least 3 prior lines of therapy for advanced ovarian cancer and who have no evidence of deleterious or suspected deleterious *gBRCA* mutation(s) as defined by a local test conducted in an appropriately accredited laboratory (eg, Clinical Laboratory Improvement Amendments [CLIA]-certified) that includes comprehensive DNA sequencing and large rearrangement analysis of *BRCA1* and *BRCA2*. Prior antiangiogenic treatment such as bevacizumab, either in a first line or a recurrent setting is optional. To be eligible to enter the study, all patients should have measurable disease (as assessed by the Investigator), defined as at least 1 lesion that can be accurately assessed at baseline by computed tomography (CT)/ magnetic resonance imaging (MRI) and is suitable for repeated assessment per RECIST 1.1. All patients will have RECIST 1.1 tumour assessments at screening (within 28 days prior to the start of study treatment) and every 8 weeks (± 1 week) after start of treatment until objective radiological disease progression or withdrawal of consent. Objective radiological response on treatment (complete response [CR] or PR) will need to be confirmed

during next RECIST 1.1 visit assessment to ensure that identified responses are not a result of measurement error in a single arm clinical trial.

Patients will receive the combination of:

- Cediranib tablets 30 mg oral once daily
- Olaparib tablets 200 mg oral twice daily

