5.1 Efficacy assessments

5.1.1 Tumor assessments by CT or MRI scans

Radiological assessment should use the same modality of imaging throughout the trial. Contrast-enhanced CT scan is preferred but MRI is acceptable where CT is contraindicated. Please refer to the Image Acquisition Guidelines and Site Operations Manual for a quick reference guide for image acquisition and data handling.

Baseline tumor assessment should include CT/MRI of the chest, abdomen and pelvis within 28 days prior to the start of IPs. Follow-up CT/ MRI tumor assessments will cover chest (in those patients with disease in the chest or upper abdomen lymphadenopathy at baseline), abdomen and pelvis with any other regions imaged at baseline where disease was present. Any other sites at which new disease is suspected should also be appropriately imaged. Radiological examinations performed in the conduct of this study should be retained at site as source data. Copies of all imaging assessments including unscheduled visit scans will be collected on an ongoing basis and sent to Contract Research Organization (CRO) for ICR (see Section 5.1.3).

All treatment decisions will be based on Investigator assessment of scans. All patients will have RECIST 1.1 tumor assessments at screening (within 28 days prior to the date of first dose of IPs) and thereafter every 8 weeks (± 1 week) relative to the date of first dose of IPs (Table 5) until objective radiological disease progression as defined by RECIST 1.1 and as determined by the Investigator, or unless they withdraw consent. Objective radiological response on treatment (CR or PR) will need to be confirmed during next RECIST 1.1 visit assessment.

If a patient discontinues IPs for any reason other than disease progression or withdrawal of consent, RECIST 1.1 assessments should continue as per protocol schedule until evidence of objective radiological progression or withdrawal of consent (see Section 4.3).

It is important to follow the assessment schedule as closely as possible. If scans are performed outside of scheduled visit (± 1 week window) and the patient has not progressed, every attempt should be made to perform the subsequent scans at their scheduled time points.

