8.4.1 Primary Endpoint

Objective Response Rate (ORR)

ORR is defined as the number (%) of patients with measurable disease at baseline, with at least one visit response of CR or PR that is confirmed at least 4 weeks later. For the primary analysis ICR is required for both the initial response and confirmation. Data obtained up until progression, or last evaluable assessment in the absence of progression, will be included in the assessment of ORR. However, any CR or PR which occurred or was confirmed after a further anticancer therapy was received will not be included in numerator of the ORR calculation. In the case where a patient has two non-consecutive visit responses of PR or CR, then, as long as the time between the 2 visits of PR or CR is greater than 4 weeks and there is no PD between the PR visits, the patient will be defined as a responder. Note that CR followed by PR is classed as progression.

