While disease progression may require confirmation, it is not mandated in this study. Confirmation will be subject to the investigator's discretion (eg. if investigator is not sure of progression at initial assessment). The confirmatory scan should occur preferably at the next scheduled visit and no earlier than 4 weeks after the initial assessment of progression of disease (PD) in the absence of clinical deterioration.

If a patient discontinues treatment (and/or receives a subsequent cancer therapy) prior to progression then the patient should still continue to be followed until objective disease progression.

CONFIRMATION OF RESPONSE

In Study D8488C00001, imaging for confirmation of response (CR or PR) should be performed at the next scheduled RECIST assessment, 8 weeks (certainly no less than 4 weeks) following the date the criteria for response were first met.

CENTRAL REVIEW

The Contract Research Organisation appointed by AstraZeneca to perform the independent central review for the primary analysis of this study will provide specification for radiological imaging protocols in standard acquisition guidelines documentation.

REFERENCES

Eisenhauer et al 2009

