1.2 Study design

This is an open label, Phase IIb, single arm, multi-center study to assess the efficacy and safety of the combination of cediranib and olaparib in platinum resistant relapsed high grade serous, high grade endometrioid or clear cell ovarian, fallopian tube or primary peritoneal carcinoma who have received at least 3 prior lines of chemotherapy and who have no evidence of deleterious or suspected deleterious *gBRCA* mutation(s) as defined by a local test conducted in an appropriately accredited laboratory (e.g., Clinical Laboratory Improvement Amendments [CLIA]-certified) that includes comprehensive DNA sequencing and large rearrangement analysis of *BRCA1* and *BRCA2*. All patients should have received prior antiangiogenic treatment e.g. bevacizumab, either in a first line or a recurrent setting. To be eligible to enter the study, all patients should have measurable disease (as assessed by the Investigator), defined as at least 1 lesion that can be accurately assessed at baseline by computed tomography (CT)/ magnetic resonance imaging (MRI) and is suitable for repeated assessment per RECIST 1.1. All patients will have RECIST 1.1 tumor assessments at screening (within 28 days prior to the start of study treatment) and every 8 weeks (± 1 week) after start of treatment until objective radiological disease progression or withdrawal of consent. Objective radiological response on treatment (complete response [CR] or PR) will need to be confirmed during next RECIST 1.1 visit assessment to ensure that identified responses are not result of measurement error.

Patients will receive the combination of:

- Cediranib tablets 30 mg oral once daily
- Olaparib tablets 200 mg oral twice daily

Patients should continue to receive IPs until objective radiological disease progression, unacceptable toxicity or withdrawal of consent.

The study originally planned to recruit 100 patients over approximately 12 months. Due to slower than projected recruitment, the study now plans to recruit approximately 60 patients. An interim futility analysis will be undertaken once the first 20 evaluable (by Investigator assessment) patients have received at least 1 dose of IP and have had opportunity to be followed for at least 4 months. If fewer than 4 radiological tumor responses are observed at this point, the trial may be considered futile and stop enrollment. Enrollment will continue whilst the futility analysis is being conducted.

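### The confirmation rule for the primary ORR is internally inconsistent: a PR-SD-PR or PR-NE-PR patient is a responder by the endpoint text and a non-responder by SAP Table 6

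*SAP*

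**What the plan says.** **Next-visit wording.** SAP 1.2 says a CR or PR "will need to be confirmed during next RECIST 1.1 visit assessment to ensure that identified responses are not result of measurement error". Protocol 1.4 has the same requirement and reason: "during next RECIST 1.1 visit assessment to ensure that identified responses are not a result of measurement error in a single arm clinical trial". Protocol 5.1.1 repeats it without the reason: "Objective radiological response on treatment (CR or PR) will need to be confirmed during next RECIST 1.1 visit assessment". Protocol Appendix F says that imaging to confirm a response "should be performed at the next scheduled RECIST assessment, 8 weeks (certainly no less than 4 weeks" after the response criteria were first met.

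**Non-consecutive wording.** Protocol 8.4.1 opens its exception with "In the case where a patient has two non-consecutive visit responses of PR or CR, then, as long as the time between the 2 visits" and sets the condition "as long as the time between the 2 visits of PR or CR is greater than 4 weeks and there is no PD between" the two. SAP 3.2.1 has a parallel sentence for "two non-consecutive visit responses of PR, then, as long as the time between the 2 visits of PR is greater than 4 weeks", again excluding only PD in between. It adds that CR-NE-CR more than 4 weeks apart gives a best response of CR.

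**Table 6.** SAP 3.2.1 then introduces Table 6 as "the rules that will be followed to determine whether such patients would be counted in the numerator of ORR for the primary analysis", and as the source of best objective response (BoR). The table has a first and a second time point only. PR then SD is No for confirmed response, with BoR SD. PR then NE is No, with BoR SD or NE depending on the minimum SD duration. CR then NE is also No.

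No sentence says which text prevails, or how Table 6 applies when a further response follows the SD or NE.

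**The concern.** SAP 3.1 says the RECIST outcomes are calculated programmatically for both central and site data, so one rule has to be coded. For a patient with PR, then SD or NE, then PR, the rules disagree about whether she enters the primary numerator. BoR is offered as support for ORR. If the text is used for ORR and the table for BoR, the same patient can be an ORR responder with a best response of SD.

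The duration-of-response population follows the same choice. SAP 3.2.2 starts DoR at the first response that is later confirmed, so a PR-SD-PR patient would enter with the SD interval counted as response time.

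The stated reason for confirmation also matters. A tumour measured close to the 30% shrinkage line can move between PR and SD through measurement variation alone, which is what the next-visit wording is meant to guard against.

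**Working it through.** **Inputs.** About 60 patients (Protocol 1.4; SAP 1.2); prior Beta(1/3, 1/3) (Protocol 8.2 and 8.5.1); at least 4 follow-up scans per patient by data cut-off (Protocol 8.1). The size of the evaluable-for-response set is not given, so 60 is used as the denominator, as an assumption.

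**1. Reproduce the plan's own figures.** The posterior is P(ORR≥t) = 1 − F(t; 1/3+x, 1/3+n−x), with F the beta distribution function.
- 30/100: 0.991 for t=20% and 0.947 for t=23% (plan: >99% and 94.6%).
- 26/100: 0.927 for t=20% (plan: >90%).
- Beta-binomial predictive probability of at least 30/100 after 3/20: 4.57% (plan: ≤4.6%).

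The model matches the plan's. None of these figures depends on the confirmation rule.

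**2. Score the sequences under each source.**

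| Sequence | Next-visit wording (Protocol 1.4, 5.1.1; SAP 1.2) | SAP Table 6, first two visits | Endpoint text (Protocol 8.4.1; SAP 3.2.1) |
|---|---|---|---|
| PR-PR | responder | Yes, BoR PR | responder |
| PR-SD-PR | not confirmed | No, BoR SD | responder |
| PR-NE-PR | not confirmed, read literally | No, BoR SD or NE | responder |
| CR-NE-CR | not confirmed, read literally | No, BoR SD or NE | responder, BoR CR |

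**3. Count the patterns that disagree.** Take every sequence of PR, SD, NE and PD over 4 visits, ending at the first PD. There are 121. Two successive PRs occur in 27; two PRs anywhere occur in 41. So 41 − 27 = 14 patterns are scored differently: 8 have SD between the two PRs (for example PR-SD-PR-PD, PR-SD-SD-PR and SD-PR-SD-PR) and 6 have only NE between them. These count patterns. They are not probabilities.

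**4. Effect of one patient.** 1/60 = 1.7 ORR points. With n=60:

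| Responders | ORR | P(ORR≥20%) |
|---|---|---|
| 15 | 25.0% | 0.827 |
| 16 | 26.7% | 0.894 |
| 17 | 28.3% | 0.939 |
| 18 | 30.0% | 0.967 |

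If the evaluable set is smaller, one patient has a similar effect: 0.848 to 0.913 for 13 to 14 of 50, and 0.837 to 0.903 for 14 to 15 of 55.

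**5. What is not affected.** The interim futility count includes unconfirmed responses, so it is the same under either rule.

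**The case against.** The best case for the plan is that its operative definitions agree. Protocol 8.4.1 and SAP 3.2.1 are where the numerator is defined in words, and both accept non-consecutive responses. SAP 3.2.1 also gives a general test of repeat imaging at least 4 weeks later with no progression in between, and Protocol 8.5.1 asks only for 4 weeks. The next-visit sentences sit in design and assessment sections, and Appendix F suggests they may concern scan timing. Table 6 covers two time points and cannot be a full algorithm: the paragraph above it gives CR-NE-CR a best response of CR, so text must supplement table somewhere. SAP 3.2.2 derives BoR from all data up to first progression, which would make PR-SD-PR a PR in both outputs.

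Much of this stands. A programmer would probably code the non-consecutive rule. But the design sections state a requirement and give a reason, and Table 6 claims to decide the numerator in the same section as the text it contradicts. The reconciling reading has to be inferred.

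Three stronger readings are tempting but not supported:
- **One patient could turn a failed trial into a success by crossing 0.90.** The design criterion paired P(ORR≥20%)>0.9 with an observed 30/100, and neither part is restated for 60. At 26.7% and 28.3%, both illustrative results fall below 30% if that part is carried over as a rate. The primary analysis only reports posterior probabilities.
- **The looser rule adds 13 to 19 points.** Those are differences in the chance of confirmation for a hypothetical borderline patient: 35% against 22% at a per-visit PR chance of 0.3, and 69% against 50% at 0.5. They assume 4 independent visits and no PD or dropout. They are not a change in trial ORR.
- **The rule will be chosen with the results in view.** The study is open-label, but the primary reading is by two independent radiologists with adjudication, and their results are not communicated to investigators. Nothing in the documents shows a data-driven choice.

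The planned ICR analysis of confirmed plus unconfirmed responses bounds ORR from above. It does not show ORR under the other confirmation rule.

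**Conclusion.** The inconsistency is real and concerns the primary endpoint. The same central readings can give two ORR numerators, and with them two BoR tables and two DoR populations. The cause is unreconciled wording. The documents do not show that the ORR will in fact differ.

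The numerators differ only if at least one patient has two responses separated by SD or NE and no successive pair. The documents give no basis for that number. Each such patient moves ORR by about 1.7 points, taking 60 as the denominator. The posterior figures (0.894 at 16/60, 0.939 at 17/60) illustrate sensitivity to one responder and do not mark a decision boundary. That SD may lie between the two responses is itself an inference, because the text excludes only PD.

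Two smaller mismatches belong to the same repair. The protocol's exception covers PR or CR, while the SAP's covers PR and bridges CR only over NE. A gap of at least 4 weeks also stands beside one of more than 4 weeks.

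**What to change.** Before database lock:

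1. State one confirmation rule in the same words in Protocol 1.4, 5.1.1 and 8.4.1 and in SAP 1.2, 3.2.1 and Table 6. Say whether SD, or only NE or missing visits, may lie between the two responses, whether the rule treats CR and PR alike, and whether the gap is at least or more than 4 weeks. Either choice on SD can be defended: the two endpoint definitions currently allow it, and the measurement-error reasoning argues against it. It needs to be fixed in advance.
2. Add PR-SD-PR, PR-NE-PR and CR-NE-CR rows to Table 6, so that the ORR numerator equals CR+PR in the BoR table and matches the patients analysed for DoR.
3. Report ORR under the other rule as one sensitivity row.

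The cost is aligned wording in the two documents, three table rows and one output row. The downside is that ORR may be slightly lower if the stricter rule is chosen.

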3.2.2 Secondary endpoints

Duration of response (DoR)

DoR will be defined as the time from the date of first documented response (which is subsequently confirmed) until date of documented progression or death in the absence of disease progression (ie, date of PFS event or censoring – date of first response + 1). The end of response should coincide with the date of progression or death from any cause used for the PFS endpoint. The time of the initial response will be defined as the latest of the dates contributing towards the first visit that was CR or PR that was subsequently confirmed.

If a patient does not progress following a response, then their DoR will use the PFS censoring time.

Disease control rate

Disease control rate is defined as the percentage of patients who have a best overall response of CR or PR or SD (at 6 months). For SD to be counted, patients should have demonstrated SD for a minimum interval of 23 weeks (24 weeks minus 1 week to allow for an early assessment within the assessment window, ie, 161 days) following the start of treatment.

Progression free survival (PFS)

PFS is defined as the time from date of first dose until the date of objective disease progression or death (by any cause in the absence of progression) regardless of whether the patient withdraws from study therapy or receives another anti-cancer therapy prior to progression (i.e. date of PFS event or censoring – date of first dose + 1). Patients who have not progressed or died at the time of analysis will be censored at the time of the latest date of assessment from their last evaluable RECIST assessment. However, if the patient progresses or dies after two or more missed RECIST assessments visits, the patient will be censored at the time of the latest evaluable RECIST assessment prior to the two missed visits.

If the patient has no evaluable visits or does not have baseline data they will be censored at Day 1 unless they die within 2 visits of baseline (16 weeks plus 1 week allowing for a late assessment within the visit window).

The PFS time will always be derived based on scan/assessment dates not visit dates. RECIST assessments/scans contributing towards a particular visit may be performed on different dates. The following rules will be applied:

- For ICR assessments, the date of progression will be determined based on the **earliest** of the scan dates of the component that triggered the progression for the adjudicated reviewer selecting PD or of the reviewer who read baseline first if there is no adjudication for ICR data.

- For Investigator assessments, the date of progression will be determined based on the **earliest** of the dates of the component that triggered the progression.
- For both ICR and investigator assessments, when censoring a patient for PFS the patient will be censored at the **latest** of the dates contributing to a particular overall visit assessment.

Note: for TLs only the latest scan date is recorded out of all scans performed at that assessment for the TLs and similarly for NTLs only the latest scan date is recorded out of all scans performed at that assessment for the NTLs.

Overall visit assessments will be determined for each assessment (scheduled or unscheduled) and will contribute to the derivation of PFS. Objective disease progression is defined as: at least a 20% increase in the sum of the diameters of the target lesions (compared with a previous minimum sum) and an absolute increase of >5 mm, an overall assessment of progression or a new lesion.

Overall survival (OS)

Overall survival is defined as the time from the date of first dose until death due to any cause regardless of whether the patient withdraws from treatment or receives another anti-cancer therapy (i.e. date of death or censoring – date of first dose + 1). Any patient not known to have died at the time of analysis will be censored based on the last recorded date on which the patient was known to be alive.

Survival calls will be made in the 2 weeks following the date of the data cut-off for the primary analysis, and if patients are confirmed to be alive (or if the death date is post the relevant data cut-off date) these patients will be censored in the associated analyses at the date of the data cut off. Data will be recorded on the SURVIVE module of the eCRF and this dataset will be used as priority for analysis.

For the OS analysis for the primary analysis at the 8 month DCO the Date last known alive on survival status CRF (SURVIVE: SUR_DAT) will be used.

If this date is missing the last date for each individual patient is defined as the latest among the following dates recorded on the case report forms (CRFs):

- AE start and stop dates (AE: AESTDAT, AEENDAT)
- Admission and discharge dates of hospitalization (SERAE: AESHODAT, AESDIDAT)
- Study treatment date (EX & EX1: EXSTDAT)
- End of treatment date (EX & EX1: EXENDAT)

28(56)

89 of 118

- Laboratory collection dates (LB & LB1-6: LBDAT)
- Date of vital signs (VS & VS1: VSDAT)
- Disease scan dates on RECIST CRF (1,3RECIST1: R1ASMDAT)
- Start and stop dates of alternative anticancer treatment (CAPRX1: CXSDAT, CXEDAT)
- Start and stop dates of post-IP radiotherapy (CAPRXR1: CXRDSDAT, CXRDEDAT)
- End of study date (DS: DSSTDAT)
- Visit date (VISIT: VIS_DAT)

The status of ongoing, withdrawn (from the study) and “lost to follow-up” patients at the time of the final OS analysis should be obtained by the site personnel by checking the patient’s notes, hospital records, contacting the patient’s general practitioner and checking publicly-available death registries. In the event that the patient has actively withdrawn consent to the processing of their personal data, the vital status of the patient can be obtained by site personnel from publicly-available resources where it is possible to do so under applicable local laws.

Best objective response (BoR)

Best objective response (BoR) is calculated based on the overall visit responses from each RECIST assessment, described in section 3.1.3. It is the best response a patient has had following start of treatment, but prior to starting any subsequent cancer therapy and up to and including RECIST progression or the last evaluable assessment in the absence of RECIST progression. Categorisation of BoR will be based on RECIST using the following response categories: CR, PR, SD, PD and NE.

CR or PR must be confirmed. For determination of a best response of SD, the earliest of the dates contributing towards a particular overall visit assessment will be used. SD should be recorded at least 8 weeks minus 1 week, i.e. at least 49 days (to allow for an early assessment within the assessment window), after start of treatment. For CR/PR, the initial overall visit assessment which showed a response will use the latest of the dates contributing towards a particular overall visit assessment.

BoR will be determined programmatically based on RECIST from the overall visit response using all ICR data up until the first progression event. It will also be determined programmatically based on RECIST using all site investigator data up until the first progression event. The denominators for each case will be consistent with those used in the ORR analysis.

For patients who die with no evaluable RECIST assessments, if the death occurs ≤ 9 weeks (i.e. 8 weeks + 1 week to allow for a late assessment within the assessment window) after start of

treatment, then BoR will be assigned to the progression (PD) category. For patients who die with no evaluable RECIST assessments, if the death occurs > 9 weeks after start of treatment then BoR will be assigned to the NE category.

Time to discontinuation of IPs or death (TDT)

Time to discontinuation of IPs or death is defined as the time from the date of first dose of IP to the earlier of the date of discontinuation of both IPs, or death date. Both IPs should be discontinued at the same time but in rare circumstances discontinuation of one of the IPs before the other may be allowed. In such a case, TDT will reflect the time from the date of first dose to the earliest IP discontinuation date.

Any patient not known to have died at the time of analysis and not known to have discontinued study treatment will be censored based on the last recorded date on which the patient was known to be alive.

